5.3 LIFESTYLE CONSIDERATIONS

N/A

5.4 SCREEN FAILURES

Screen failures are defined as participants who consent to participate in this study but are not subsequently assigned to the study intervention or entered in the study. Individuals who do not meet the criteria for participation in this trial (screen failure) because of meeting one or more exclusion criteria (e.g., development of an exclusionary health condition) will not be rescreened.

5.5 STRATEGIES FOR RECRUITMENT AND RETENTION

Potential participants will first be identified using the electronic medical record (EMR). Specifically, we will identify patients age 65 and older with diagnosis codes for knee or hip OA (M17.0, M17.10, M17.11, M17.12, M17.2, M17.30, M17.31, M17.32, M17.4, M17.5, M17.9, M16.0, M16.10, M16.11, M16.12, M16.2, M16.30, M16.31, M16.32, M16.4, M16.50, M16.51, M16.52, M16.6, M16.7, M16.9, M19.90, M19.91, M19.92, M19.93, M15.0 (primary, generalized OA)), a diagnosis code for at least one qualifying comorbid health condition under CCM guidelines listed above, and no diagnosis codes for exclusionary health conditions. We will include patients who have been seen within UNC by a primary care provider during the past 2 years, including Internal Medicine, Family Medicine and Geriatrics clinics. Primary care providers may, if they choose, review lists of patients eligible based on the EMR and approve a final list of patients to contact, but this is not a requirement. These patients will be mailed an introductory letter and then called by a study team to further assess eligibility. Patients who are eligible and interested in participating will complete a verbal consent process which will include verbal HIPAA authorization. Then participants will complete baseline assessments via telephone and be mailed an accelerometer for physical activity assessment. Participants will be paid \$25 for completing each phone-based assessment and \$15 for returning the accelerometer at each time point. Following return of the accelerometer at baseline, an unblinded study team member will call the participant to inform them of their randomization assignment. Participants assigned to the OA-PCP group will then be mailed an Activity Tracker and instructions and asked to begin wearing it as soon as they receive it. About a week after the Activity Tracker is mailed, an unblinded study team member will call the participant to answer any questions about device wear and setup. We will aim for the participant to wear the Activity Tracker for at least 1 week prior to the first OA-PCP call, so that PA goals can be based on current activity patterns. Participants will also be notified that the PA Coach will be able to view their Activity Tracker data using Fitabase®.

Participants in both the intervention and control group will have regular contact with an interventionist throughout the study period. Based on our prior studies, we believe this will enhance retention. In addition, we believe that the lack of requirement for any in-person study visits will enhance both recruitment and retention. To facilitate completion of recruitment calls, as well as baseline and follow-up assessment calls, we will call participants on different times of day and different days, across multiple weeks. We have used this strategy successfully in prior studies to reach participants at times convenient to them.

6.0 STUDY INTERVENTIONS

6.1 STUDY INTERVENTION ADMINISTRATION

OA-PCP Intervention

As summarized in Figure 3, the OA-PCP will include four phases, with a total intervention period of 12 months.

[figure not shown]

Figure 3. OA Physical activity Care Pathway

Phase 1: Physical Activity Screening

This component of the OA-PCP will be completed as described above within the recruitment and enrollment process. Although it is framed within the recruitment process here, it has been designed to mirror a PA screening process that could occur routinely in primary care.

Phase 2: Brief Initial PA Counseling

This will be delivered via phone by the PA Coach, who will be trained in relevant aspects of PA and motivational interviewing. The content for the initial call is designed to be brief enough that it can be embedded within a routine CCM call; future calls are even shorter. We have developed detailed scripts for all OA-PCP calls. The following are key components of the first PA counseling call:

1. *Description of the Benefits and Appropriateness of PA for OA:* This content includes a brief summary of benefits of PA and basic information for safe, appropriate PA in the context of OA. With regard to aerobic activity, the PA Coach will encourage participants that good long-term goals are to do 150 minutes of moderate intensity activity per week and or 7,500-10,000 steps per day, per general public health recommendations and recent research evidence^{76,77}. However, the Coach will also stress the value and health benefits of interim goals when increasing amount of weekly aerobic activity. In addition, goal-setting for aerobic activity will be framed around benchmarks of particular relevance for people with OA, as described below. With respect to strengthening exercises, participants will be encouraged to perform these at least twice per week on non-consecutive days⁷⁸. Lower extremity strengthening exercises will be emphasized. Participants will be encouraged to perform stretching exercises daily. Instructions and example strengthening and stretching exercises are included in the Arthritis Foundation brochure described below.

2. *PA Goal-Setting:* The Coach will work with participants to establish and document PA goals, with an initial focus on the next 2 weeks (before check-in call; Figure 3). Participants will be asked to focus their PA goals on either step counts or activity minutes; monitoring for each of these will be facilitated by use of the Activity Trackers. Recent research has identified important metrics for reducing risks of functional limitation and disability among individuals with OA. In particular, thresholds of 60 weekly minutes of MVPA and 6,000 steps per day as important targets^{79,80}. Participants will be asked to select one of these benchmarks as a minimum goal to work toward during the one-year time period of the intervention. If participants meet one of these goals, they will be encouraged to work toward broader public health goals of 150 minutes of MVPA per week or 7,500-10,000 steps per day^{76,77}. Participants may also switch from step-focused goal to an activity minute-focused goal as the OA-PCP calls progress. As noted above, initial goals will be based on participants' current PA data (e.g., at least 1 week of Activity Tracker wear). The PA Coach will inform participants that s/he will be able to monitor their PA (using Fitabase®), with their permission, based on data from the Activity Tracker, and describe that this will enhance the "partnership" of this program, allowing the Coach to observe specific PA patterns and potential opportunities to enhance activity during the day. As part of the goal-setting process, the Coach will talk with participants about potential barriers and use a problem-solving approach to address each one.

3. *Discussion of Preferences for PA and Identifying Appropriate PA Resources:* The Coach will ask participants brief questions to understand types of PA they enjoy most and are likely to engage in. Based on this information, at the 2-week call, the Coach will recommend specific PA programs resources that can help them progress toward their PA. The coach will also review participants' progress toward PA goals and set new goals. If participants have encountered any barriers to PA since the first call, they will be addressed and other PA resources identified if needed.

4. *Follow-up emails:* The study team will ask participants to opt-in (or opt-out) to receive follow-up emails at 1-month and 2-month time points after the initial call. The content of the emails will be based on individual PA goals set during previous check in calls.

Phase 3: Linkage to PA Programs and Resources

There are a large number of OA-appropriate, evidence-based PA resources, and a collection of these resources has been developed (and is updated on an ongoing basis) by the OAAA at UNC; a key source for informing this collection is the CDC's Compendium of Arthritis Appropriate Physical Activity and Self-Management Education Interventions. Table 1 shows representative examples of these resources, which include tools to facilitate individual PA, as well as group-based classes. With regard to the latter, we will perform an environmental scan for programs available within the communities surrounding study clinics; this will be facilitated by the OAAA, the Arthritis Foundation's Online Resource Finder and the Evidence-Based Leadership Council. Based on our prior experience³⁸, there are many free, appropriate PA programs available in communities, including walking groups and classes in senior centers.

Local resource information will be used to tailor patient handouts. Participants will be able to contact the PA Coach throughout the intervention period if they have questions about PA resources, or if they would like information on different resources. We will document the frequency and nature of the contacts to inform and refine the intervention.

Table 1. Example OA-Appropriate PA Resources and Programs	
Self-Directed	
Walk With Ease (Self-Directed)	Resources to help people with arthritis learn to walk safely and regularly. Tools include a guidebook, walking diary, example exercises, interactive online resources (starting point test, motivational tools, activity log) and a mobile app. COST: Free
Exercises for Chronic Conditions	Exercise CDs developed by Stanford University, appropriate for people with arthritis and other chronic health conditions. COST: \$10

Arthritis Foundation Online PA Tools	Resources including arthritis-friendly exercise videos, workouts, tips for people with arthritis. COST: Free
Group-Based	
Arthritis Foundation Exercise Program	Community-based exercise program; trained instructors cover a variety of range-of-motion and endurance-building activities and health education topics. COST: Free or low cost, varies by location
Walk with Ease (Group-Delivered)	Community-based walking program developed by the Arthritis Foundation with regular meetings, facilitated by trained leaders. COST: Typically free
Fit and Strong	Community-based PA and behavior change intervention offering stretching, balance, and aerobic exercises. COST: Typically free at Senior Centers
Tai Chi for Arthritis	Group classes available at many YMCAs and other community centers. COST: Varies from low cost to free
Arthritis Foundation Aquatic Program	Group classes led by a trained instructor, including joint range of motion, breathing, and light aerobic activities. Many community aquatic centers have similar, appropriate programs for older adults. COST: Varies based on location, some free

Phase 4:

PA

Counseling Follow-Up

The PA Coach will call participants at three month intervals following the initial call (e.g., 3-, 6-, 9- and 12 months), again using our developed phone scripts and tailored based on earlier calls. These calls will focus on reviewing progress toward PA goals, PA patterns observed in Fitabase®, identifying additional PA resources if needed, and working with participants to set new PA goals as they progress. During the 3-month call, the coach will briefly review instructions for strengthening and stretching exercises, to complement step or activity minute goals. During the 6-month call, the PA Coach will provide tips for identifying setbacks in PA and work with participants to identify strategies for dealing with these. In between phone calls, the PA Coach will continue to send emails to participants on a monthly basis. These will focus on encouragement toward PA goals, encouragements based on data in Fitabase® and personalized tips based on these data.

Motivational interviewing (MI) principles will be used throughout the PA coaching calls. MI is a key behavior change strategy that can elicit participants' own motivations and / or ambivalence toward PA⁸¹⁻⁸³. This helps individuals to explore and resolve their own, sometimes conflicting attitudes toward changing PA behaviors, building autonomy and internal awareness that is essential for long-term behavior change. To support topics discussed during the phone calls, participants will be mailed and/ or emailed materials including: 1) handouts describing appropriate exercise for people with osteoarthritis, tips on PA for people with arthritis (including pain management), instructions for different types of exercise (aerobic, strengthening, stretching), and example exercises. 2) A list of PA programs and resources adapted for their locality. 3) Worksheets for documenting PA goals.

Attention Control Intervention

We chose this type of control group to account for the effect of general attention provided by the PA Coach. This group will receive an intervention in the same "dose" (e.g., number and duration of phone calls and emails) as the OA-PCP group, but the content will not be PA-specific. During the first call, the Coach will discuss 2 topics, for which the amount of content parallels call #1 for the OA-PCP: What is OA? OA Diagnosis and OA Risk Factors. During the second call, the Coach will discuss the topic of Health Care Providers and Overview of OA Treatment Guidelines. Call topics for 3, 6, 9 and 12- month follow-up calls will be: Pain Medications, Mechanical Treatments (e.g., knee braces, footwear, joint protection), Complimentary and Alternative Therapies and discussion of OA and Mental Health, Sleep and Fatigue. Participants will be emailed or mailed (based on their preference) handouts with information on additional topics related to OA. The study team will ask participants to opt-in to receive follow-up monthly educational emails; if they prefer, they can receive this information via mail.

6.2 FIDELITY

PA Coach(es) will be trained by [name] and will conduct mock sessions of all OA-PCP calls prior to study initiation. We plan to audio record calls for approximately the first 10 participants and a random subset thereafter. [name] and another investigator with experience in delivering behavioral PA interventions ([name] or [name]) will review audio recordings and provide feedback to the PA Coach. A similar process will be used for the attention control calls, with a particular emphasis on ensuring that OA-PCP content is not included in these calls.

6.3 MEASURES TO MINIMIZE BIAS: RANDOMIZATION AND BLINDING

The randomization scheme will be generated by the study statistician and stored within the study database. The database will be configured so that blinded study personnel (e.g., those conducting follow-up assessments) will not have access to randomization information. The participants will not be notified of randomization assignment until all baseline assessments are complete. In addition, an individual participant's randomization assignment will not be known to any study personnel until baseline assessments are complete. Randomization will be stratified according by clinic site.

6.4 STUDY INTERVENTION ADHERENCE

The study database will be used to track participants' completion of all assessment visits, as well as all intervention contacts. The coordinator will also maintain close communication with PA coach(es) regarding intervention delivery. If participants miss intervention calls, an unblinded study team member may assist the PA coach in attempting to reach the participant.

6.5 CONCOMITANT THERAPY

Participants will be permitted to continue any other OA treatment during the course of the study.

7 STUDY INTERVENTION/ DISCONTINUATION AND PARTICIPANT DISCONTINUATION/WITHDRAWAL

7.1 DISCONTINUATION OF STUDY INTERVENTION

When a participant discontinues from the OA-PCP or attention control intervention but not the study, remaining study procedures (e.g., follow-up assessments) will be completed as indicated by the study protocol. If a clinically significant finding is identified after enrollment (e.g. health-related changes that may change the safety level of participating in an independent PA program), the investigator or qualified designee will determine if any change in participant management is needed. Any new clinically relevant finding will be reported as an adverse event (AE). The data to be collected at the time of study intervention discontinuation will include the reason(s) for discontinuing the participant from the intervention, and methods for determining the need to discontinue.

7.2 PARTICIPANT DISCONTINUATION/WITHDRAWAL FROM THE STUDY

Participants are free to withdraw from participation in the study at any time upon request.

An investigator may discontinue a participant from the study for the following reasons:

- Lost-to-follow up; unable to contact subject
- Any event or medical condition or situation occurs such that continued collection of follow-up study data would not be in the best interest of the participant or might require an additional treatment that would confound the interpretation of the study
- The participant meets an exclusion criterion (either newly developed or not previously recognized) that precludes further study participation

The reason for participant discontinuation or withdrawal from the study will be recorded in the study database. Participants who discontinue or are withdrawn will be replaced up to the point of randomization assignment being given to the participant. Once participants are given their randomization assignment, they will be counted toward the total study sample size and not replaced.

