9.3 POPULATIONS FOR ANALYSES

The primary analyses will be conducted using an intent-to-treat approach. Supportive exploratory analyses may be conducted to consider samples with greater completion of study intervention visits. Since this is an exploratory trial, the nature of these supportive analyses will be based on observed patterns of intervention contacts.

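### Section 7.2 permits removal of a randomised participant from the study for a possible confounding treatment or a precluding exclusion criterion, and the available text provides for no outcomes afterwards

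*Combined protocol and SAP*

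**What the plan says.** Section 7.2 lists reasons for which an investigator may discontinue a participant from the study. Two matter here.

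- **Confounding treatment.** An event, condition or situation that "might require an additional treatment that would confound the interpretation of the study".
- **Exclusion criterion.** "The participant meets an exclusion criterion (either newly developed or not previously recognized) that precludes further study participation". The plan does not say which criteria preclude participation.

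Neither ground is limited to the time before randomisation. Of participants who have been told their assignment, the section says "they will be counted toward the total study sample size and not replaced". It adds: "The reason for participant discontinuation or withdrawal from the study will be recorded in the study database".

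Section 7.1 has the remaining assessments completed when a participant "discontinues from the OA-PCP or attention control intervention but not the study". It also leaves participant management to the investigator when there are "health-related changes that may change the safety level of participating in an independent PA program". Section 6.5 states: "Participants will be permitted to continue any other OA treatment during the course of the study".

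On analysis, Section 9.3 says: "The primary analyses will be conducted using an intent-to-treat approach". Section 9.4 specifies a linear mixed model on all available data. It adds multiple imputation under a not-at-random scenario, using pattern-mixture models, if missingness is found to relate to measured patient factors.

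**The concern.** An intent-to-treat comparison needs outcomes whatever treatment or health change comes later. Removing someone because a later treatment would complicate interpretation selects on an event after randomisation. So does removal for a newly met exclusion criterion.

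Either event may relate to arm or outcome. Recent significant lower-extremity injury is an exclusion criterion (5.2), and injury is a listed risk of exercise (2.2.1), which only one arm is coached to increase. Repeated falls and planned joint replacement are further criteria that can arise later and bear on activity.

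For outcomes never collected, the mixed model relies on their being missing at random given the data it uses. Removal for a new treatment or health condition is a reason to doubt that. The loss is partly avoidable, because follow-up is by phone and mailed accelerometer (8.1). Section 9.2 says the estimates will inform a larger trial, so avoidable bias matters here even without a claim of significance.

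**Working it through.** **1. Does any section restore outcomes after a 7.2 removal?**

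| Section | What it covers | Restores MVPA or WOMAC? |
|---|---|---|
| 7.1 | Leaving the intervention but not the study | No |
| 7.2 | Recording the reason; no replacement | No |
| 7.3 | Missed contacts and loss to follow-up | No |
| 8.3.4 | Adverse event recording for 7 or 30 days after participation | No |
| 9.3, 9.4 | Analysis of what was collected; conditional imputation | No |

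Section 7.2 does not state that measurement stops. That follows from removal being from the study, from the contrast with 7.1, and from the reference in the same 7.2 item to continued collection of follow-up data.

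**2. Is the decision blinded?** Section 6.3 gives follow-up assessors as its example of blinded staff. No available section blinds the investigator who decides. The text of 10.1.5, on key roles, was not available, so this cannot be put more strongly.

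**3. The plan's own figure.** Section 9.2 states about 80% power for an effect size of 0.38 with 120 per group and 10% attrition. With 120 × 0.90 = 108 per arm, power is 79.7% (normal approximation) or 79.4% (t-test). The figure reproduces. The issue is possible bias, not sample size.

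**4. Illustration of size.** Removal rates and outcome gaps are not in the documents, so these are assumptions:

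- removal on these grounds of 5% in one arm against 2% or 0% in the other, within the 10% allowance;
- later MVPA of those removed differing from those retained by a gap of 0.5 to 1.0 SD, in the same direction in both arms and not explained by baseline.

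Standard error of the difference = √(2/108) = 0.136 SD. The 95% half-width = 1.96 × 0.136 = 0.267 SD.

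*Removed before 6 months:* shift = rate difference × gap.
- 5% vs 2%: 0.03 × 0.5 = 0.015; 0.03 × 1.0 = 0.030 SD.
- 5% vs 0%: 0.05 × 0.5 = 0.025; 0.05 × 1.0 = 0.050 SD.

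*Removed after a 6-month visit that already shows the change:* with equal correlation ρ between visits, the model recovers part of the gap and the shift becomes shift/(1 + ρ). For ρ from 0.5 to 0.7:
- 5% vs 2%: 0.015/1.7 = 0.009 to 0.030/1.5 = 0.020 SD.
- 5% vs 0%: 0.025/1.7 = 0.015 to 0.050/1.5 = 0.033 SD.

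*Largest value against precision:* 0.050/0.136 = 0.37 of the standard error; 0.050/0.267 = 19% of the half-width; 0.050/0.38 = 13% of the effect size in 9.2.

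**5. What continued follow-up would gain.** If a random fraction r of those removed before 6 months is still measured, bias per arm = p × gap × [1 − r/(1 − (1 − r)p)], where p is the removal rate. With r = 0.5 and gap 1.0:
- p = 0.05: 0.05 × (1 − 0.5/0.975) = 0.0244.
- p = 0.02: 0.02 × (1 − 0.5/0.99) = 0.0099.

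The shift falls to 0.0244 − 0.0099 = 0.0145 SD (5% vs 2%) or 0.0244 SD (5% vs 0%). At gap 0.5 the values are 0.0072 and 0.0122 SD.

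**The case against.** The strongest reply is that the plan already limits the problem in several ways.

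- The power is permissive, and reasons are recorded.
- Other OA treatment may continue (6.5), and pain medication is itself an exploratory outcome (8.1), so removal merely for added OA treatment is unlikely to be routine.
- An injury can be handled under 7.1, where stopping only the intervention keeps follow-up in place.
- Section 9.4 plans a not-at-random sensitivity analysis that speaks directly to the feared harm.
- The illustrated effect is small. Recovering half of those removed changes the estimate by about 0.008 to 0.026 SD (0.015 − 0.0072 to 0.050 − 0.0244), or 0.06 to 0.19 standard errors, in a trial sized on feasibility.

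Most of this stands and limits the severity. It does not close the gap. The 7.1 route does not bar use of 7.2. The 9.4 analysis is conditional, is not tied to 7.2 removals and cannot recover data never collected. A recorded reason explains a loss without restoring the outcome.

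Two stronger readings are tempting and not supported. A reader might infer that 7.2 contradicts the intent-to-treat set in 9.3. It does not: randomised participants stay in the count, and the 9.4 model uses their earlier data. A reader might also infer that meeting any exclusion criterion is enough for removal. The text requires one that precludes further participation; the narrower gap is that such criteria are not named.

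**Conclusion.** The point holds as a design weakness of low to moderate severity. Following 7.2 as written can cause avoidable loss of outcomes for reasons that may relate to arm or outcome, and the available text provides for no MVPA or WOMAC measurement afterwards. This rests on the inference that discontinuation from the study ends outcome collection.

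The documents do not support a claim that the result will be biased. They give no removal rates or outcome gaps, so size and direction are unknown and the bias may be zero. On the assumed inputs it is at most about 0.05 SD, or 0.37 of the standard error. The case for acting is that the remedy is cheap and that lost outcomes cannot be recovered at analysis.

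**What to change.** - Delete the confounding-treatment wording in 7.2 as a ground for ending follow-up, and reconcile 7.2 with 6.5.
- State that meeting an exclusion criterion after randomisation does not by itself end outcome collection.
- Attempt the scheduled 6- and 12-month accelerometer and phone measures for all randomised participants. The exceptions are those who withdraw, cannot be contacted, fall under the existing best-interest wording, lack capacity to consent, or cannot complete the measures. In the last case, collect whatever remains possible, for example the mailed accelerometer when a phone interview is not.
- Include all collected outcomes in the primary analysis.
- Use the recorded discontinuation reasons in the sensitivity analysis already planned in 9.4. An analysis by additional treatment would be limited to the arthritis medications recorded under 8.1, because the measures described there do not systematically record other treatments.

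Whether the intervention continues stays with the investigator under 7.1.

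**Cost.** Protocol wording, slightly more analysis, and a few assessments already scheduled. On the assumed rates, 120 × 0.05 = 6 to 120 × (0.05 + 0.02) = 8.4 participants are affected. Over two visits that is at most about 12 to 17 remote assessments. At $25 + $15 = $40 per time point (5.5), this is about $480 to $680, which would be paid anyway if no one were removed.
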